## **Final version**

- Total troponin I release (area under the curve) during the first four days after surgery (stratified on cardiac troponin I and high-sensitive troponin I)
- Perioperative myocardial infarction
- Major adverse cardiovascular events (30 days)
- Length of postoperative hospital stay
- Intensive care unit admission
- All-cause mortality (30 days)

To analyze the association between the intervention and the primary outcome, myocardial injury, we will do a univariate and multivariate logistic regression. The results will be expressed as odds ratios (95% confidence interval).

The decision to include a variable in the multivariate logistic regression will be based on clinical hypotheses. Trial site effect will be analyzed. A maximum of one variable per 10 primary events will be included.

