#### *Recruitment*

All patients hospitalized to undergo emergent or urgent major noncardiac surgery at Department of Orthopedic Surgery, Zealand University Hospital, Department of Orthopedic Surgery, Holstebro Hospital, and Department of Orthopedic Surgery, Herlev Hospital, will as far as possible be screened to determine whether they meet the inclusion and exclusion criteria.

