### Plasma cardiac troponin I

Plasma cTnI will be analyzed at the local department of biochemistry using Siemens Healthcare Dimension Vista (Zealand University Hospital, Herlev Hospital), Abbott high-sensitive troponin I (Holstebro Hospital).

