**Secondary analyses**

All analyses compare the difference between the intervention group and the control group. Continuous outcomes will be analyzed with non-parametric (Wilcoxon two-sample test) or parametric statistics (unpaired t-test) depending on data distribution and equality of variances. If necessary data will be logarithm transformed. Continuous outcomes will be expressed as mean (95% confidence interval) or median (inter-quartile range). Categorical outcomes will be analyzed with a chi-square test or Fischer's exact test (an expected count < five in one cell) and the result will be expressed as no. (%). Differences are considered significant if the two-sided p-value < 0.05.

Secondary comparisons include

- Peak plasma troponin I within four days of surgery (stratified on cardiac troponin I and high-sensitive troponin I)

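### Length of stay is compared with a test that pools three hospitals; stratifying by hospital would recover precision at almost no cost

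*Combined protocol and SAP*

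**What the plan says.** The Secondary analyses section of the final SAP sets one rule: "Continuous outcomes will be analyzed with non-parametric (Wilcoxon two-sample test) or parametric statistics (unpaired t-test) depending on data distribution and equality of variances". "Length of postoperative hospital stay" is then listed with no stratum, covariate or model of its own.

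The Recruitment section of the current protocol names three recruiting units: "Department of Orthopedic Surgery, Zealand University Hospital, Department of Orthopedic Surgery, Holstebro Hospital, and Department of Orthopedic Surgery, Herlev Hospital".

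Hospital appears as an analysis factor in one place in the final SAP, the paragraph that begins "To analyze the association between the intervention and the primary outcome, myocardial injury, we will do a univariate and multivariate logistic regression" and goes on to state "Trial site effect will be analyzed". That paragraph concerns the primary outcome only. Two secondary outcomes, peak troponin and total troponin release, are stratified by assay. The section on plasma cardiac troponin I assigns the high-sensitive assay to Holstebro alone, so this split separates Holstebro from the other two hospitals, but it does not apply to length of stay.

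The Allocation and blinding section describes a computer-generated list and sealed envelopes. It does not say whether allocation is stratified by hospital.

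**The concern.** Of the listed secondary outcomes, length of stay is among the most likely to depend on the hospital itself, through discharge routines and access to rehabilitation. Case mix may add to this. The earlier protocol, at a single hospital, also admitted major general surgery, which the third protocol amendment removed on the date Herlev was added. If any such patients were enrolled, they would be concentrated at the first site.

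A pooled test leaves between-hospital variation in the error term. If allocation is not balanced within hospital, a chance excess of one arm at a long-stay hospital also moves the observed difference. The test's error rate allows for that, but the estimate from this particular trial is still shifted. What is at stake is a somewhat higher chance of missing a real difference in stay. The validity of the test is not in question.

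**Working it through.** **The plan's own figure.** The SAP powers only myocardial injury: 15% versus 7%, two-sided 5%, power 80%, 264 per arm. Without continuity correction, n = [1.96·√(2·0.11·0.89) + 0.8416·√(0.15·0.85 + 0.07·0.93)]² / 0.08² = 238.9, that is 239. With the correction, n = (238.9/4)·[1 + √(1 + 4/(238.9·0.08))]² = 263.4, that is 264. The stated figure reproduces, but it says nothing about length of stay, for which the plan states no power.

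**Inputs for length of stay.** From the documents: 270 per arm, three hospitals, two-sided 5%. Not in the documents, so assumed: the spread of stay, hospital shares, differences between hospitals and the treatment effect.

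**Calculation 1: spread within hospital held fixed.** Simulated stay is rounded to whole days (minimum 1), with median 7 days at the reference hospital, log SD 0.6 within hospital and a log treatment effect of −0.15 (exp(−0.15) = 0.86, 14% shorter). Hospital shares are 50/30/20% or 60/30/10%. Allocation is 270:270, not stratified by hospital. There were 3,000 trials per power scenario and 2,000 under the null.

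| Ratio of stay between hospitals | Share of log variance due to hospital | Power, plain Wilcoxon | Power, van Elteren |
|---|---|---|---|
| 1 / 1 / 1 | 0% | 80% | 80% |
| 1 / 1.2 / 0.9 | 2.5–3.0% | 79–80% | 80–81% |
| 1 / 1.3 / 0.8 | 5.9–7.6% | 78–79% | 80–81% |
| 1 / 1.5 / 0.7 | 13–17% | 74–76% | 80–81% |

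The second column follows from the ratios. For 1/1.5/0.7 with shares 50/30/20%, the mean log ratio is 0.3·0.405 − 0.2·0.357 = 0.050. The between-hospital variance is 0.3·0.164 + 0.2·0.127 − 0.050² = 0.072, and the share is 0.072/(0.072 + 0.36) = 16.7%. Type I error was near 5% for both tests. The Monte Carlo standard error of one power estimate is √(0.8·0.2/3000) = 0.7 points.

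**Calculation 2: total spread held fixed.** Let R² be the share of variance due to hospital. The pooled comparison has 80% power at a difference of (1.96 + 0.8416)·√(2/270) = 0.241 SD. Adjusting for hospital gives power Φ(2.8016/√(1−R²) − 1.96), equivalent to an unadjusted trial of 270/(1−R²) per arm. A second simulation used log-normal stay, shares 60/20/20% or equal, allocation with and without balance by hospital, and 3,000 trials per scenario.

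| R² | Adjusted power (formula) | Equivalent n per arm | Simulated plain Wilcoxon | Simulated van Elteren |
|---|---|---|---|---|
| 0% | 80.0% | 270 | 77–79% | 77–79% |
| 5% | 82.0% | 284 | 77–79% | 78–81% |
| 10% | 84.0% | 300 | 77–79% | 81–82% |
| 20% | 88.0% | 338 | 78–82% | 86–87% |

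**If allocation was balanced within hospital.** The plain test then becomes conservative: its type I error is about 3.7–3.9% at R² = 10% and 2.9% at 20%, while the stratified test stays near 5%. The pooled test therefore gives up precision under either form of allocation.

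**The case against.** The strongest reply is that nothing here is incorrect. The SAP names its tests, its summaries and its significance level, and a two-sample test after randomisation is standard. The loss exists only if hospitals differ in stay, and no part of the documents shows that they do. Recruitment has been confined to hip surgery since August 2015, which narrows one source of difference. Under moderate assumptions the gain is 1 to 3 points, and the 5 to 7 point figure needs a 1.5/0.7 = 2.1-fold difference between the longest-stay and shortest-stay hospitals. The outcome is secondary and unpowered. All of this stands, and it is why the point is minor.

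Further limits also stand. Hospital strata do not remove variation by type of surgery within a hospital, and they do not deal with death before discharge. The simulations assumed the same treatment effect at every hospital. A van Elteren test yields a p-value and no estimate, so an estimator has to be named too. The same remark could be made of other outcomes; stay is singled out because it most plausibly depends on local practice.

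None of this favours the pooled test. In every scenario examined, stratifying cost no power beyond simulation error, including when hospitals did not differ. The SAP already accepts the principle by stratifying two outcomes by assay and examining site for the primary outcome.

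**Conclusion.** The point holds as a minor one. The final SAP leaves hospital out of the length-of-stay comparison although it is known for every patient. The planned test is valid, and the cost is lost precision: from nothing to about 7 points of power on the first set of assumptions, with the upper end an extreme case, and about 2 to 8 points if hospital explains 5% to 20% of the variance in stay with total spread held fixed. These figures rest on assumed spread, effect, hospital shares and hospital differences, so confidence in the size is low. The direction is more secure: stratifying helps if hospitals differ and does no measurable harm if they do not.

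**What to change.** In the Secondary analyses section of the final SAP, state that length of postoperative stay will be compared with a Wilcoxon test stratified by the three hospitals (van Elteren), or, if the log scale is chosen, with a linear model of log stay that includes treatment and hospital. Name the matching estimate: a hospital-stratified Hodges–Lehmann difference with the first option, or the hospital-adjusted ratio of geometric means with the second, each with a 95% confidence interval. State in the protocol whether allocation was balanced within hospital.

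The cost is a sentence or two in the SAP. Hospital is already recorded, and no further patients or data are needed. The change should be dated before unblinding; after that it should be reported as a labelled supportive analysis.

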## **Sample size**

We predict that 15% of the patients in the placebo group will suffer from myocardial injury and that the incidence of myocardial injury will be reduced to 7% in the intervention group. Type I error is set at 5% and type II error is set at 20%. In total 2 x 264 patients need to be included based on this power calculation. We will include patients until we have a total of 2 x 270 patients for evaluation (per-protocol).

**Summary of Changes**  
**Statistical Analysis Plan**

| Amendment, date      | Details  |
|-----------------------------|---|
| 1. Amendment,
04.06.2015 | Peak plasma troponin I and total troponin I release (area under the curve): The analyses will be stratified on cardiac troponin I and high-sensitive troponin I   |
| 2. Amendment,
25.01.2016 | We decided not to perform the interim analysis.
No data analysis had been performed and the investigators were blinded.  |
| 3. Amendment,
01.09.2017 | The addition of a univariate and multivariate logistic regression to analyze the association between the intervention and the primary outcome. The analyses were added before the study inclusion was terminated. No data analysis had been performed and the investigators were blinded. |
